11. PHARMACOVIGILANCE

11.1 DEFINITIONS

Adverse Event (AE): Any untoward medical occurrence in a patient or clinical trial subject, administered a medicinal product and, which does not necessarily have a causal relationship with this treatment. *An AE can therefore be any unfavourable and unintended sign (including an abnormal laboratory finding), symptom, or disease temporally associated with the use of an investigational medicinal product (IMP), whether or not considered related to the IMP.*

Adverse Reaction (AR): All untoward and unintended responses to an IMP related to any dose administered. *All AEs judged by either the reporting investigator or the sponsor as having reasonable causal relationship to a medicinal product qualify as adverse reactions. The expression 'reasonable causal relationship' means to convey, in general, that there is evidence or argument to suggest a causal relationship.*

Unexpected Adverse Reaction: An AR, the nature or severity of which is not consistent with the applicable product information (e.g. Investigator's brochure for an unapproved investigational product or summary of product characteristics (SmPC) for an authorised product). *When the outcome of the adverse reaction is not consistent with the applicable product information, this*

adverse reaction should be considered as unexpected. Side effects documented in the SmPC which occur in a more severe form than anticipated are also considered to be unexpected.

Serious Adverse Event (SAE) or Serious Adverse Reaction: Any untoward medical occurrence or effect that at any dose:

- Results in death

- Is life-threatening – *refers to an event in which the subject was at risk of death at the time of the event; it does not refer to an event which hypothetically might have caused death if it were more severe*
- Requires hospitalisation, or prolongation of an existing inpatient hospitalisation
- Results in persistent or significant disability or incapacity
- Is a congenital anomaly or birth defect

Medical judgement should be exercised in deciding whether an AE/AR is serious in other situations. Important AE/ARs that are not immediately life-threatening or do not result in death or hospitalisation but may jeopardise the subject or may require intervention to prevent one of the other outcomes listed in the definition above, should also be considered serious.

Suspected Unexpected Serious Adverse Reaction (SUSAR): any suspected adverse reaction related to an IMP that is both unexpected and serious.

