7.1 STUDY OUTCOME MEASURES

Primary endpoints:

- number, timing and severity of adverse events in the MSC treatment group will be compared to the placebo group;
- total number of GEL counted over month 1, 3 and 6 will be compared between treatment groups.

[figure not shown]
Secondary endpoints:

- volume of GEL identified over months 1, 3 and 6 will be compared between treatment groups.
- number of GEL counted over months 7, 9 and 12 (crossover re-treatment) compared between treatment periods (placebo vs. active treatment) for each patient.
- combined unique MRI activity (number of new or enlarging T2, or enhancing or re-enhancing lesions).
- number of relapses in MSC treatment group vs. placebo group in the first 6 months and after crossover re-treatment in the two groups (see below for the definition of a relapse).
- time to sustained progression of disability (RRMS group) (see below for definition of sustained EDSS progression) and proportion of progression-free patients.

- proportion of disease-free patients (i.e. patients without relapses) and progression of MRI activity in the two groups.
- changes in the Multiple Sclerosis Functional Composite (MSFC) score in MSC treatment group compared to the placebo group.
- effect of MSCs on the peripheral immune responses (for patients in the first phase of recruitment).
- effect of MSCs on delayed type hypersensitivity (Type 1V hypersensitivity) reaction as measured by the Mantoux test.

Given the exploratory nature of MSC use, no specific quantitative assumptions have been made about the outcomes measures.

[figure not shown]
Figure 1: Patient flow and study outline

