11.3 REPORTING PROCEDURES

All adverse events should be reported (Figure 3). Depending on the nature of the event, the reporting procedures below should be followed. Any questions concerning adverse event reporting should be directed to the study coordination centre in the first instance. A flowchart is given below to aid with the reporting procedures.

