11.3.2. Serious AR/AEs

Fatal or life threatening SAEs and SUSARs should be reported on the day that the local site is aware of the event. The SAE form requests the following information on any event: the nature of the SAE, the date of onset, the severity, corrective therapies given, the outcome and causality (i.e. unrelated, unlikely, possible, probably, definitely). The responsible investigator should sign the causality of the event. Additional information should be sent within 5 days if the reaction has not resolved at the time of reporting.

SAEs

An SAE form should be completed and faxed to the study coordination centre for all SAEs within 24 hours. However, death from an unrelated cause (e.g. road traffic accident), MS relapses and hospitalisations for elective treatment of a pre-existing condition do not need reporting as SAEs.

SUSARs

In the case of suspected unexpected serious adverse reactions, the staff at the site should:

- Complete the SAE case report form & send it as soon as possible (within 24 hours and preferably by fax), signed and dated to the study coordination centre together with relevant treatment forms and anonymised copies of all relevant investigations.

[figure not shown]
Or

- Contact the study coordination centre by phone and then send the completed SAE form to the study coordination centre within the following 24 hours as above.

The study coordination centre will notify the MHRA, REC and the Sponsor of all SUSARs occurring during the study according to the following timelines; fatal and life-threatening within 7 days of notification and non-life threatening within 15 days. All investigators will be informed of all SUSARs occurring throughout the study.

Figure 3. Safety reporting overview

Safety Reporting Overview

* Unless identified in the protocol as not requiring immediate reporting

Contact details for reporting SAEs and SUSARs

Fax: **xxx**, attention **xxx**

Please send SAE forms to: **xxx**

Tel: **xxx** (Mon to Fri 09.00 – 17.00)

Figure 4. Schedule of study assessments and treatments

	Screening - 10 weeks (±7 days)	- 8 weeks (±7 days)	- 8 weeks (±7 days)	- 2 weeks (±14 days)	Week 0	Week 0	Week 4 (±7 days)	Week 8 (±7 days)	Week 12 (±7 days)	Week 16 (±7 days)	Week 20 (±7 days)	Week 24 (±7 days)	Week 28 (±7 days)	Week 32 (±7 days)	Week 36 (±7 days)	Week 40 (±7 days)	Week 44 (±7 days)	Week 48 (±7 days)	Week 48 (±7 days)
Informed Consent	x	x																	
Inclusion/exclusion review	x	x			x														

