13. STATISTICS AND DATA ANALYSIS

13.1 RATIONALE

The main aim of each national trial participating in this international collaborative effort, including the present one, is to assess the feasibility, safety and the toxicity of MSC infusion, as administered within this specific treatment protocol, in active MS. To fulfill this aim, all randomised patients receiving at least one MSCs infusion (or infusion media) will be followed for at least two years after the last study drug administration. All adverse events will be recorded and compared in the two treatment groups. Comparative analyses of the incidence of new GEL at MRI acquired on conventional 1.5 T MRI scans over 24 weeks will be conducted as well, to provide preliminary data on the activity of the experimental treatment. However, the main analyses of safety, toxicity and activity will be those on the entire data set obtained by pooling the results of all national trials, for an expected total of 160 randomised patients.

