13.3 EVALUATION OF PRIMARY OUTCOME VARIABLES

- Primary outcome: To assess the safety of intravenous therapy with autologous MSCs in MS patients. The safety of MSCs infusion will be evaluated including frequency, timing and severity of any adverse events in both MSCs and placebo treatment groups. A statistical comparison of the number of adverse events between treatment groups will be carried out using a chi-square test.
- Co-Primary outcome: To assess the activity of autologous MSCs in MS patients. The total number of gadolinium-enhancing lesions (GEL) at MRI at week 4, 12 and 24 will be compared between treatment groups using a Negative Binomial (NB) regression analysis, adjusting for the number of GEL at baseline.

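### MS relapses fall inside the adverse-event count tested between arms, so a relapse benefit from MSC would make that test understate an excess of other events

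*Combined protocol and SAP*

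**What the plan says.** All references are to the combined protocol and SAP.

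- **Definition (11.1).** An adverse event includes "any unfavourable and unintended sign (including an abnormal laboratory finding), symptom, or disease temporally associated with the use" of the investigational product, whether or not it is thought related. Relapse and MS worsening are not excepted.
- **Reporting (11.3, 11.3.1, 11.3.2).** "All adverse events should be reported", and non-serious events go on the case report form. The only exemption for relapses concerns serious events: "MS relapses and hospitalisations for elective treatment of a pre-existing condition do not need reporting as SAEs".
- **Endpoint and test (7.1, 13.1, 13.3).** The first primary endpoint is that "number, timing and severity of adverse events in the MSC treatment group will be compared to the placebo group". Section 13.1 adds: "All adverse events will be recorded and compared in the two treatment groups". In 13.3 the outcome covers "frequency, timing and severity of any adverse events in both MSCs and placebo treatment groups", and the one formal test is: "A statistical comparison of the number of adverse events between treatment groups will be carried out using a chi-square test". Events are not restricted by type or by causality.
- **Relapses as efficacy (6.2, 7.1, 13.4).** The number of relapses by arm is a secondary endpoint, analysed by negative binomial regression. Relapses are documented on the e-CRF (8.4) and defined in 12.3.1.

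**The concern.** The same event is used twice with opposite meaning: as an efficacy outcome that MSC is hoped to reduce, and as a unit in the primary safety count. Patients are selected for active disease, so relapses during the first 24 weeks are to be expected. If MSC prevents some of them, the AE total in the MSC arm falls for a reason unrelated to tolerability, and that fall offsets any rise in infusion-related or other non-MS events. What is at stake is the only planned formal test of the first primary outcome: a result near no difference could not be read as absence of added harm.

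**Working it through.** **The plan's own figure.** No sample size or power is stated for the AE comparison. The only stated calculation is for lesions (13.2): 160 pooled patients, 80% power, 5% level, mean 7.4, SD 11.4, 50% decrease. A two-sided negative binomial log-rate formula reproduces it:

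- dispersion k = (11.4² − 7.4)/7.4² = 2.238
- n per arm = (1.960 + 0.842)² × (1/7.4 + 1/3.7 + 2 × 2.238)/(ln 0.5)² = 79.7, so 80 per arm and 160 in total

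That figure is not affected by this point. It supplies the 80 per arm used below; 1:1 allocation is assumed because no ratio is stated.

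**Inputs for the AE comparison.** Section 7.1 says that no quantitative assumptions were made about the outcomes, so all of these are assumptions:

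- r, relapses per placebo patient over 24 weeks: 0.3 to 0.5. The one anchor is the RRMS entry criterion of at least one relapse in 18 months: 24/78 weeks = 0.31. It is a selection criterion, not a forecast of the on-study rate.
- relapses halved by MSC (the 50% in 13.2 is for lesions, not relapses)
- b, non-MS AEs per placebo patient: 1, 2 or 3
- true ratio of non-MS AEs, MSC to placebo: 1.25

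**All-AE ratio** = (1.25b + 0.5r)/(b + r):

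| b | r = 0.3 | r = 0.5 |
|---|---|---|
| 1 | 1.40/1.30 = 1.08 | 1.50/1.50 = 1.00 |
| 2 | 2.65/2.30 = 1.15 | 2.75/2.50 = 1.10 |
| 3 | 3.90/3.30 = 1.18 | 4.00/3.50 = 1.14 |

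With more frequent non-MS events the distortion shrinks: b = 4 gives 1.20 and 1.17, and b = 6 gives 1.21 and 1.19.

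**When the totals cancel.** The arms are equal when the excess of non-MS events per patient equals r × the relative reduction in relapses. If the reduction in relapses is larger than the excess, the all-AE ratio falls below 1.

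**No effect on relapses.** The ratio is then (1.25b + r)/(b + r). For b = 1 and r = 0.5 it is 1.75/1.50 = 1.17, which is dilution only.

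**Effect on the test.** This takes a two-sided 5% test on event totals A and B, with equal exposure and Poisson counts. With d = |B − A|/√(A + B), power = Φ(d − 1.96) + Φ(−d − 1.96).

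*Case b = 1, r = 0.5 halved, non-MS AEs 1.0 v 1.25:*
- 80 per arm, relapses excluded: 80 v 100 events, d = 20/√180 = 1.49, power 32%
- 80 per arm, relapses counted: 120 v 120, power 5% (the alpha level)
- 80 per arm, relapses counted, no effect on relapses: 120 v 140, d = 20/√260 = 1.24, power 24%
- 11.5 per arm (23 UK patients): 9% excluded, 5% counted

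*Larger case, 1.0 relapse halved, non-MS AEs 1.0 v 1.5:*
- 80 per arm: 81% excluded, 5% counted, and 56% if counted with no effect on relapses
- 11.5 per arm: 19% excluded, 5% counted

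If the chi-square is instead read as comparing patients with at least one AE, the cancellation is the same. At 80 per arm, power is 19% excluded v 5% counted in the first case, and 52% v 5% in the larger one. Overdispersion would lower the power figures but would not remove the cancellation.

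**The case against.** **Inclusion is inferred.** A reader might take the protocol to say outright that relapses are AEs. It does not, and several places treat the two apart: 12.2.2 has one rule for relapse visits and another for adverse effects, 9.4.1 names disease exacerbation alongside adverse events, 11.2 and 11.3.1 speak of toxicities, and relapses have their own documentation (8.4) and definition (12.3.1). This stands as a limit. Even so, the 11.1 definition covers a relapse, and an exemption from SAE reporting would be needless if relapses were not AEs. If sites did code relapses differently, the pooled count would mix two definitions.

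**Other displays would show harm.** The outcome also covers timing and severity, causality is graded (11.2), infusion toxicity within three hours has its own definition (10.6), relapses are analysed by arm (13.4), and a safety committee reviews the side-effect profile of both arms (15.3). This largely stands: the damage is to the single formal comparison, not to the whole safety assessment. Causality grading is the weaker safeguard, since it falls to the investigator responsible for care and the treating team is unblinded (9.3).

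**The rates are assumed.** This stands. Equality appears in one of the six cells, 15.3 thinks a large effect unlikely, and frequent non-MS AEs, including abnormal laboratory findings, would shrink the distortion.

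**Few UK patients.** With up to 23 patients the test has little power however AEs are counted. This stands too, so the effect lies mainly in the pooled analysis of 160 patients, which 13.1 calls the main one.

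**An all-AE comparison is legitimate.** It is, but it answers a different question from whether MSC adds harm apart from its effect on the disease. Both can be reported.

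**Conclusion.** The point holds as a weakness in the primary safety comparison. Following the plan as written counts an efficacy event inside the only formal safety test. Under the assumed rates, a true 25% excess of non-MS events would appear as an all-AE ratio of 1.00 to 1.18, nearer to 1.25 when non-MS AEs are more frequent. The direction depends on MSC lowering relapses; without that effect there is dilution only.

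Two stronger conclusions are not supported. One is that the arms will come out equal: this needs the relapse reduction to match the added harm, and the protocol gives no rates from which to judge that. The other is that harm would go unseen: severity, timing, causality, infusion toxicity and relapses by arm are all examined separately. The change is worth making before analysis because it is cheap and the comparison is a primary one.

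**What to change.** In 13.3, state that:

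- the between-arm AE comparison is made on AEs other than events recorded as relapses on the e-CRF that meet the 12.3.1 definition;
- a sensitivity analysis also removes recorded relapses that do not meet that definition, which 12.3.1 already analyses separately;
- the all-AE comparison is reported beside it;
- relapses and other MS worsening are tabulated by arm as a separate safety display, so that worsening on MSC stays visible.

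MS progression and ambiguous MS symptoms should stay in the AE count. Progression under 12.3.2 needs a 6-month sustained EDSS increase, which can hardly be confirmed in the 24 weeks before crossover, and 9.4.1 treats disease exacerbation on MRI as a safety signal. SAE reporting does not change. The same rule should be carried into the pooled analysis.

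The cost is one additional analysis and one table. No new data are needed: relapses are already on the e-CRF (8.4), their definition rests on EDSS changes, and the EDSS assessors are blinded (9.3). No new blinded classification of AEs is required.

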11.2 CAUSALITY

Most adverse events and adverse drug reactions that occur in this study, whether they are serious or not, will be expected treatment-related toxicities due to the drugs used in this study. The assignment of the causality should be made by the investigator responsible for the care of the participant using the definitions in the table below. If any doubt about the causality exists, the local investigator should inform the study coordination centre which will notify the Chief Investigator. Other clinicians may be asked to advise in some cases. In the case of discrepant views on causality between the investigator and others, all parties will discuss the case. In the event that no agreement is made, the MHRA will be informed of both points of view.

Relationship	Description
Unrelated	There is no evidence of any causal relationship.
Unlikely	There is little evidence to suggest there is a causal relationship (e.g. the event did not occur within a reasonable time after administration of the trial medication). There is another reasonable explanation for the event (e.g. the participant's clinical condition, other concomitant treatment).
Possible	There is some evidence to suggest a causal relationship (e.g. because the event occurs within a reasonable time after administration of the trial medication). However, the influence of other factors may have contributed to the event (e.g. the participant's clinical condition, other concomitant treatments).
Probable	There is evidence to suggest a causal relationship and the influence of other factors is unlikely.
Definitely	There is clear evidence to suggest a causal relationship and other possible contributing factors can be ruled out.
Not assessable	There is insufficient or incomplete evidence to make a clinical judgement of the causal relationship.

11.3 REPORTING PROCEDURES

All adverse events should be reported (Figure 3). Depending on the nature of the event, the reporting procedures below should be followed. Any questions concerning adverse event reporting should be directed to the study coordination centre in the first instance. A flowchart is given below to aid with the reporting procedures.

11.3.1. Non-serious AR/AEs

All such toxicities, whether expected or not, should be recorded in the toxicity section of the relevant case report form and sent to the study coordination centre within one month of the relevant AR/AE.

11.3.2. Serious AR/AEs

Fatal or life threatening SAEs and SUSARs should be reported on the day that the local site is aware of the event. The SAE form requests the following information on any event: the nature of the SAE, the date of onset, the severity, corrective therapies given, the outcome and causality (i.e. unrelated, unlikely, possible, probably, definitely). The responsible investigator should sign the causality of the event. Additional information should be sent within 5 days if the reaction has not resolved at the time of reporting.

SAEs

An SAE form should be completed and faxed to the study coordination centre for all SAEs within 24 hours. However, death from an unrelated cause (e.g. road traffic accident), MS relapses and hospitalisations for elective treatment of a pre-existing condition do not need reporting as SAEs.

SUSARs

In the case of suspected unexpected serious adverse reactions, the staff at the site should:

- Complete the SAE case report form & send it as soon as possible (within 24 hours and preferably by fax), signed and dated to the study coordination centre together with relevant treatment forms and anonymised copies of all relevant investigations.

[figure not shown]
Or

- Contact the study coordination centre by phone and then send the completed SAE form to the study coordination centre within the following 24 hours as above.

The study coordination centre will notify the MHRA, REC and the Sponsor of all SUSARs occurring during the study according to the following timelines; fatal and life-threatening within 7 days of notification and non-life threatening within 15 days. All investigators will be informed of all SUSARs occurring throughout the study.

Figure 3. Safety reporting overview

Safety Reporting Overview

* Unless identified in the protocol as not requiring immediate reporting

Contact details for reporting SAEs and SUSARs

Fax: **xxx**, attention **xxx**

Please send SAE forms to: **xxx**

Tel: **xxx** (Mon to Fri 09.00 – 17.00)

Figure 4. Schedule of study assessments and treatments

	Screening - 10 weeks (±7 days)	- 8 weeks (±7 days)	- 8 weeks (±7 days)	- 2 weeks (±14 days)	Week 0	Week 0	Week 4 (±7 days)	Week 8 (±7 days)	Week 12 (±7 days)	Week 16 (±7 days)	Week 20 (±7 days)	Week 24 (±7 days)	Week 28 (±7 days)	Week 32 (±7 days)	Week 36 (±7 days)	Week 40 (±7 days)	Week 44 (±7 days)	Week 48 (±7 days)	Week 48 (±7 days)
Informed Consent	x	x																	
Inclusion/exclusion review	x	x			x														
Medical history	x																		
Concomitant medications record	x	x	x		x	x	x	x	x	x	x	x	x	x	x	x	x	x	
Vital signs	x	x	x		x	x	x	x	x	x	x	x	x	x	x	x	x	x	
Physical exam	x	x			x		x		x		x	x		x		x	x	x	
Study treatment (MSC) infusion					x							x							
Adverse events record		x	x		x	x	x	x	x	x	x	x	x	x	x	x	x	x	
Release of MSC product				x															
Randomisation																			
Lumbar puncture	x									x								x	
Skin biopsy*	x																		
Bone marrow harvest	x																		
EDSS	x	x			x	x	x		x			x	x	x		x			x
MSIS29	x				x		x		x			x		x		x			x
MSFC	x				x							x							x
T25-FW	x				x		x		x			x		x		x			x
Quality of life/Fatigue impact scale	x				x		x		x			x		x		x			x
Hematology, Blood Chemistry	x				x		x		x		x	x	x		x		x	x	
Blood tests pre-bone marrow harvest	x																		
Pregnancy test	x				x		x		x		x	x	x		x		x	x	
Urinalysis	x				x		x		x		x	x	x		x		x	x	
Research blood samples*		x	x		x	x	x	x	x	x	x	x	x	x	x	x	x	x	
Mantoux skin test	x				x							x							x
Mantoux readout			x		x								x						x
MRI					x		x		x		x		x		x			x	
ECG	x																		

* Only part of the first phase of recruitment

